#### **10.1.4 MRI scan**

There are no known risk factors associated with MRI scans for healthy subjects except that participants may experience discomfort as they will be required to lie still in a confined area. Participants may experience claustrophobia (fear of enclosed spaces and/or anxious feelings accompanied by fast heart rate or shortness of breath) within the MRI scanner. In addition, the scanner produces a loud repetitive knocking noise during the study that some people find bothersome.

#### **10.1.5 Escitalopram**

Side effects of escitalopram include nausea, sleepiness, headache, dizziness, tremor, diarrhea, nervousness, dry mouth, increased sweating, and insomnia or ejaculation failure. Less common side effects include: rash, agitation, decreased sex drive, fatigue. Rare or uncommon side effects include: constipation, loss of appetite, vomiting, stomach upset, and vision abnormalities

#### **10.1.6 Celecoxib**

Celecoxib has been associated with an increased risk of cardiovascular events in people with cardiovascular disease (Celecoxib package insert). Side effects include nausea, diarrhea, gas, cold symptoms, sore throat, lack of energy, loss of appetite, fever, rash, back pain, and flu-like symptoms, among others. Participants would be instructed to contact study members if severe,

CONFIDENTIAL

serious, or persisting side effects occur. There is a rare risk of stroke or heart attack; however these very serious side effects are greatest risk for those with current clinically significant cardiac disease, and we are excluding these people (clinically significant cardiovascular disease usually includes one or more of the following: cardiac surgery or myocardial infarction within the last 4 weeks; unstable angina; acute decompensated congestive heart failure or class IV heart failure; current significant cardiac arrhythmia or conduction disturbance, particularly those resulting in ventricular fibrillation, or causing syncope or near syncope; uncontrolled high blood pressure; QTc greater than 450msec (by history for subjects with cardiac disease); documented prior stroke; clinically significant abnormalities on EKG.) Celecoxib also has increased risk for gastrointestinal bleeding and hepatic impairment. We will exclude those with current ulcer disease or GI bleeding as well as those with liver function impairment (as determined by a liver function test prior to entry into the study). We are excluding clinically significant cardiovascular disease for the past 6 months.

## **10.2 Minimizing risks**

The following considerations have been made in order to minimize risk as much as possible:

**Informed Consent:** All consenting procedures will be HIPAA compliant. Participants will be given a full description of all study procedures and the risks involved, and any questions the participant may have will be answered prior to consenting to the study. The consent process will be done in a private exam room.

**Clinical interview and assessment:** All clinical assessors have extensive experience in clinical psychiatric assessment and will make every effort to implement protocol procedures in a sensitive and supportive manner. Other measures to minimize risks include the careful assessment of each subject before the study, and close clinical scrutiny during all aspects of the study. There are no physical risks of diagnostic procedures or ratings.

**Blood draw:** To reduce the risks to subjects from the drawing of blood, only trained personnel will perform these procedures, and immediate medical assistance and facilities will be available at all times.

**MRI scan:** The potential risks related to MRI will be minimized in the following manner: Subjects are screened for exclusions such as foreign metallic implants and pacemakers to MRI participation prior to enrollment; claustrophobia from MRI will be reduced by explaining the nature of the magnetic resonance scanner in detail to all participants prior to their enrollment.

Subjects who have a history of claustrophobia will not be enrolled into the study. If the subject complains of feeling claustrophobic, the study will be terminated; to lessen the noise of the scanner, earplugs will be provided.

**Treatment with Escitalopram:** Participants receiving treatment with escitalopram will be monitored closely for any adverse side effects. Two-week follow-up visits will be scheduled to

CONFIDENTIAL

evaluate response to treatment and participants will be withdrawn from the study if their depressive symptoms worsen or they have intolerable side effects to escitalopram. These patients will be referred for follow-up care.

**Confidentiality:** The risk of violating confidentiality will be minimized by the following: all computer data obtained from the laboratory and from research interviews will be identified by a code number; all data will be kept in locked file cabinets and only made available to qualified research personnel; participants will be asked to provide only the contact numbers or e-mail addresses which they want us to use for study related contact. HIPAA compliance will be enforced as per

University of Pennsylvania policy and approval; reports from patients clinical records concerning research observations will not be available to outside medical facilities without the written consent of the subject; all participant interaction with the PI will occur in private exam rooms or in the PIs private office; only essential, engaged study members will interact with participants during all research activities.

**Others:** Any unanticipated findings of potential medical significance discovered during the course of this study, such as an abnormality in the MRI scan or significant deficit during neuropsychological testing, will be reported to the PI. The participant will be informed and referred to their private physician.

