**2.2 Study Design**

100 depressed and 50 control subjects, age 18-80, male and female, will be recruited for this study. Depressed participants will be stratified based on their c-reactive protein (CRP) levels (i.e., “High” CRP $\geq$ 3 and “Low” CRP<3). All participants will be started on either 10 mg of escitalopram + placebo or 10 mg of escitalopram + celecoxib (400mg/day) daily for 3 days. Following this lead-in dose of the SSRI they will then take 20 mg daily thereafter for 39 days and have no changes in their dose of placebo or celecoxib. Follow-up visits for all depressed participants will occur at 1 week, 2-weeks, and 4-weeks, following the start of treatment. The study coordinator and PI will monitor side effects and vital signs, and the PI may adjust the medication dosage depending on the patient's response to treatment and/or the presence of side effects. Final dose (10 mg versus 20 mg, or a dose between 10 mg and 20 mg, e.g., 15 mg) will be determined by clinical response and side effects. This decision will be based on an ongoing discussion between the participant and the study doctor. Participants who remit will have their end of study visit with a blood draw, and neuropsych testing at 6 weeks. Participants will then taper off medication at 10 mg for 3 days (if taking 20 mg during study). Based on past studies, less than 10% of participants will be taking less than 20 mg/day of SSRI at the end of the study.

Participants initially randomized to escitalopram + placebo, who do not remit will be treated with 6 weeks of escitalopram + celecoxib. They will not repeat the baseline visit, but will re-complete medication visits at week 1,2, and 4, After the 6 weeks of escitalopram + celecoxib they will undergo a 3rd MRI, neurocognitive session, and blood draw. Those who complete the study at this point will taper off medication at 10 mg for 3 days.

CONFIDENTIAL

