### **3.3 *Suicidal Ideation and Behavior***

Plan for assessing suicidal ideation and behavior: The drug, escitalopram, will be administered to a portion of the participants in this study. Escitalopram does interact with the central nervous system as an antidepressant. Because it is an antidepressant, it is not expected to cause or contribute to the development of suicidal ideation or behavior. However, to monitor for a potential increase in risk of suicidal thinking and behavior, a safety protocol has been developed and plans are in place to evaluate all participants for clinical worsening and suicidality throughout participation in this study.

Safety Protocol to address potential risk of clinical worsening and suicidality:

As part of this study protocol, depressed patients will be enrolled and will be receiving anti-depressant medication, escitalopram. Current suicidality at the time of consent deems potential participants as ineligible to participate, thus suicidal patients will be screened out of the study. However, it is recognized the patients could possibly experience clinical worsening and potentially become suicidal. This possibility is unlikely for those who are receiving escitalopram since this medication is an anti-depressant and it is prescribed for the specific purpose of treating depressed mood.

To address the risk of suicidality, all patients will be closely monitored and they will receive psychiatric evaluations at baseline, weeks 1, 2, 4, and 6, as well as during all of these time points during the open label phase. The Montgomery-Asberg Depression Rating Scale will be administered at each follow-up visit to evaluate the presence of depressive symptoms.

Additionally, participants will be provided with phone numbers of research staff and they will be instructed to contact the staff if clinical worsening occurs. If research staff become aware of clinical worsening or suicidality, they will immediately intervene and activate safety procedures.

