Safety procedures will include informing the principle investigator who will then meet with the participant to assess the situation. If the participant is in imminent danger to her/himself, s/he will be escorted to the emergency room for immediate care. If the patient is reluctant or unwilling to be escorted to the emergency room the principle investigator will call 911. If the patient expresses no immediate desire to hurt her/himself, but is still considered to be a potential risk, the principle investigator will provide emergency numbers such as suicide hotline phone numbers and the principle investigator will also provide referral phone numbers for psychiatric care, facilitating the scheduling of an appointment. The principle investigator will engage the participant in a contract whereby the participant will agree to utilize the suicide hotline phone number if necessary and s/he will follow through with the psychiatric appointment.

If it is believed that the clinical worsening is deemed related to participation in the study, the principle investigator will evaluate whether the medication regimen should be modified or if the participant should be withdrawn from participation.

CONFIDENTIAL

All evaluations and decisions regarding a participant's clinical worsening and or suicidality will be documented and the appropriate regulatory authorities will be notified.

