##### **4.2 Intervention Regimen**

Participants will take escitalopram (10 mg/day for 3 days and 20 mg/day for 39 days ) plus celecoxib (400 mg/day) or escitalopram (10 mg/day for 3 days and 20 mg/day for 39 days ) plus placebo for 6 weeks. Participants will be lowered to a smaller dose of the study drug, if they are unable to handle the higher dose (as determined by side effects or subjects expressing concerns about side-effects). All participants will receive a taper dose of escitalopram at 10 mg for 3 days at the completion of the study.

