## **6 Analysis Plan**

### **6.1 Data Analysis and Predictions**

At a basic level, the design of this trial is simple repeated measures design with a) two replicates (time points) b) baseline covariates and outcomes, and c) a single between-person factor (initial case-control depression status). The data collected at two time points to be included in analysis (pre- and post-treatment) will be the depression severity, inflammatory markers, resting state functional connectivity and neuropsychometric data. There have been no published studies to date examining adjuvant celecoxib and SSRI treatment in patients who simultaneously received assessment of inflammatory biomarkers. However, based on our own small pilot sample we will have greater than 85% power to detect differences in changes in IL-6 between SSRI responders and SSRI + celecoxib responders. Volumetric data and confounders to be included in the analysis will be collected at baseline. Classic models of change scores can be used where the baseline level can be controlled giving the so-called residual change score. Use of residualized change scores has several analytic advantages: (1) control for variance (the best predictor of today's value is yesterday's value), (2) statistically each subject is started at the same point. Thus, our estimation model will be extended from the classic model of change scores to a repeated measures ANOVA (analysis of variance) or mixed model repeated measures design. A joint modeling approach with mixed models for repeated measures data can be used to address within-subject variation and between-subject variation of the repeated measurements of multiple

CONFIDENTIAL

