variables such as neuropsychological measures and inflammatory markers. Generalized linear models (GLM) will be used for the baseline data. We are aware that numerous other confounders exist (such as age, race, education, statin use and gender). When a variable is identified to be related to the outcome and covariate of interest, i.e. confounder, we will adjust for it in the model of choice. A sensitivity analysis of statin and/or ARB use will be performed via analysis by statin and ARB use to determine if it is necessary to adjust or stratify by statin and ARB use. Models consider inclusion of the list of known covariates and their interaction. The importance of these models will be assessed through inspection of the change in the parameter of interest, as well as the parameter (and p-value) for the covariate. Point estimates, p-values, and confidence intervals to test the covariate of interest will be computed. Mixed model diagnostics and GLM diagnostics will be evaluated. For the continuous outcomes, we will assess if transformations exist that can bring about near normality. In addition, the impact of skew on the stability of estimates can be assessed using bootstrap methodology. For all models involving skewed predictors, we will assess the impact of the significant outliers using bootstrap and will check the linearity assumption. Other diagnostic procedures will be used to check for the validity of the GLM assumptions such as normality of the residuals and linearity assumption. Missing data problems are ubiquitous in aging research. Missing values can arise from several sources, (1) subjects are lost to follow-up, (2) missing CRFs, or (3) particular items of a CRF are skipped. We will employ multiple imputation. In this design, we have numerous indicators of outcome and predictors. The concern is that the possibility of a Type-I error is increased if a series of univariate tests is employed. Several solutions are possible in the context of this design: 1) use of Bonferroni Corrections or the less conservative extension to Bonferroni corrections 2) use of data reduction techniques like Principal Component Analysis (PCA) , and 3) use of multivariate mixed models. Based on the estimated numbers of remitters vs non-remitters we expect to enter approximately 53 subjects in Phase II. Using the estimates from Abbasi et al. (7) for serum IL-6 comparing SSRI+celecoxib to SSRI+placebo, we will have greater than 95% power by randomizing the 53 subjects between the two groups.

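### Withdrawing worsening participants from the study loses week-6 MADRS selectively; the bias is modest and largely avoidable by imputing from the interim scores already collected

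*Combined protocol and SAP*

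**What the plan says.** Section 10.2 (Minimizing risks), under treatment with escitalopram, says "participants will be withdrawn from the study if their depressive symptoms worsen or they have intolerable side effects to escitalopram". Both randomised arms take escitalopram, so the rule covers both. The wording is mandatory, it ends study participation rather than drug alone, and it sets no threshold for worsening. What follows is "These patients will be referred for follow-up care".

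Other sections are less strict. Section 3.3 says that, for worsening deemed related to participation, "the principle investigator will evaluate whether the medication regimen should be modified or if the participant should be withdrawn from participation". Section 2.2 says "the PI may adjust the medication dosage depending on" response and side effects. Section 4.2 says "Participants will be lowered to a smaller dose of the study drug, if they are unable to handle the higher dose".

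Section 2.1 lists post-treatment MADRS, adjusted for baseline MADRS, among the primary outcomes. Section 2.2 places follow-up visits at weeks 1, 2 and 4, and Section 3.3 says "The Montgomery-Asberg Depression Rating Scale will be administered at each follow-up visit to evaluate the presence of depressive symptoms". Under Section 5.2, neuropsychological tests and scans are done at baseline and week 6 only (and again at the end of the open-label phase).

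On analysis, Section 6.1 says "The data collected at two time points to be included in analysis (pre- and post-treatment) will be the depression severity", among other measures. On missing data it says "We will employ multiple imputation", without naming the variables in the imputation model.

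**The concern.** The trigger for leaving the study is the construct that the primary clinical outcome measures. If 10.2 is followed, people seen to worsen at week 1, 2 or 4 have no week-6 MADRS, and the worst outcomes are removed from the data. If celecoxib prevents some worsening, more of these outcomes disappear from the placebo arm than from the celecoxib arm. An analysis of completers, or one that imputes from baseline and week 6 alone, would then make the placebo arm look too good and understate the benefit posited in Hypothesis 2c.

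For neuropsychology and connectivity, a participant withdrawn before week 6 has no post-baseline value at all. Withdrawal for intolerance also loses week-6 data, but both arms take escitalopram and no direction of bias is claimed for it.

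**Working it through.** **Step 1: is any later assessment provided?** The final assessment is at week 6 (Section 5.2). The flow-chart (12.1) has no early-termination visit. The only later contact is an optional six-month follow-up after study completion (Section 2.2). Section 3.3 adds no assessment for those it withdraws. In the text supplied, nothing brings a withdrawn participant back for week 6.

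**Step 2: the plan's own figures.** The documents give no MADRS mean, SD or worsening rate, so there is no MADRS figure to reproduce. The IL-6 planning figure (Section 2.7) is a difference of 2.1 with SD 3.6 and 50 per arm. It needs n = 2(1.96 + 0.84)² × 3.6²/2.1² ≈ 47 per arm, so 50 is enough. Its standard error is 3.6 × √(2/50) = 0.72, used in step 6.

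**Step 3: size of the MADRS bias.** All inputs here are assumptions:
- Week-6 MADRS change is normal with SD 9, mean −10 on placebo and −13 or −14 on celecoxib.
- Means at weeks 1, 2 and 4 are 30, 55 and 80% of the week-6 value, and SDs are 60, 75 and 90%.
- Correlation between visits is r^|i−j|, with r = 0.5, 0.65 or 0.8.
- There are 50 participants per arm.
- The trigger is an interim score 8 or 5 points above baseline. Either all of those triggered are withdrawn, or half (a dose change being tried instead in the rest).

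The standard error is 9 × √(1/n₁ + 1/n₂), with each n equal to 50 less losses. It is 1.82–1.92. Change is simulated independent of baseline, so imputation from pre/post data alone gives the completer result.

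| Trigger, share withdrawn | Lost, placebo vs celecoxib | Shrinkage | Points | Standard errors |
|---|---|---|---|---|
| +8, half | 2.3–2.9% vs 1.1–1.7% | 2.3–4.0% | 0.08–0.15 | 0.04–0.08 |
| +5, half | 5.8–7.4% vs 3.3–4.8% | 3.7–6.3% | 0.12–0.24 | 0.06–0.13 |
| +8, all | 4.7–5.9% vs 2.3–3.4% | 4.9–8.5% | 0.16–0.31 | 0.09–0.17 |
| +5, all | 11.7–14.8% vs 6.7–9.6% | 8.5–14.2% | 0.27–0.54 | 0.14–0.29 |

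For a true difference of −3 with all triggered participants withdrawn, completers give −2.57 to −2.84.

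A second set of assumptions gives a similar picture. It uses baseline mean 28 and SD 5, week-4 change −8 (SD 8), week-6 change −11 (SD 9), correlation 0.8, withdrawal judged at week 4 only, and baseline-adjusted analysis. With a true −3.0, the estimate is −2.65 for a +5 trigger, a shrinkage of (3.0 − 2.65)/3.0 = 12%. If any rise above baseline counts, it is −2.29, or (3.0 − 2.29)/3.0 = 24%. With no true effect, completers show no bias.

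**Step 4: imputation with the interim scores.** Regression imputation within arm, using interim MADRS, returns −2.99 to −3.03 for a true −3 and −3.98 to −4.03 for a true −4. The second set of assumptions also returns about −3.0. The reason is that withdrawal depends on scores that are observed, so conditioning on them removes the selection.

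**Step 5: outcomes with no interim value.** Assume a true connectivity or cognition difference of 0.38 SD (the effect size in Section 2.7) and a correlation of 0.3–0.5 with week-6 MADRS change. The bias is 0.003–0.030 SD, against a standard error of about 0.2 SD.

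**Step 6: what retrieved week-6 values would estimate.** Use the step 3 set-up with a true −3 and all triggered withdrawn. Assume referred care improves week-6 MADRS by 5–10 points and celecoxib's effect is lost on stopping. The difference including retrieved values is −2.20 to −2.82, against −2.57 to −2.84 in completers. For IL-6, if 1–10% of the celecoxib arm is off drug with no remaining effect, 2.1 becomes 2.1 × 0.99 = 2.08 to 2.1 × 0.90 = 1.89, against the standard error of 0.72.

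**The case against.** The strongest reply is that the effect is small, conservative and already within reach of the named methods. In the step 3 scenarios it never exceeds 0.29 standard errors. Even if any rise above baseline triggers withdrawal, 0.71 points is under 0.4 of the no-loss standard error of 9 × √(2/50) = 1.80. It runs toward no difference. Section 6.1 already names multiple imputation and a mixed model for repeated measures, and nothing bars the interim MADRS from either. The sentence on two time points lists data to be analysed, not imputation predictors. All of this stands. It limits the size and priority of the point, but the plan still does not say that the interim scores will be used.

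Section 10.2 may also not be the operative rule. It is a risk summary, and it mentions two-week follow-up visits that do not match the schedule at weeks 1, 2, 4 and 6. Section 3.3 allows discretion, though only for worsening judged study-related. A reader might infer from 10.2 that everyone who worsens leaves the study. The documents do not support that, because they conflict and set no threshold. The consent form was not available, so it may contain a withdrawal procedure.

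Finally, bringing withdrawn participants back does not restore the on-drug comparison. Step 6 shows that it can dilute the MADRS difference by as much as, or more than, the loss it replaces. This objection stands in full and shapes the fix.

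**Conclusion.** The point holds in a limited form. Followed as written, 10.2 makes missing week-6 MADRS depend on observed worsening. An analysis that ignores the interim scores would understate a real celecoxib benefit by about 2–14%, or 0.04–0.29 standard errors, under the step 3 assumptions. The size depends on a threshold and a worsening rate that the documents do not give.

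Three stronger readings are tempting and not supported. The rule does not threaten a false positive for celecoxib, since the between-arm bias is absent when there is no effect. The loss is not beyond repair for MADRS, since imputation using the interim scores recovers the on-drug difference in simulation. And retrieving week-6 data is not a simple correction, since it estimates a different quantity. Priority is minor to moderate: the remedy is cheap, and week-6 data not collected cannot be obtained later.

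**What to change.** 1. State in Section 6.1 that the multiple imputation model, or a mixed model, includes the week 1, 2 and 4 MADRS scores, by arm. This is one sentence and needs no new data.
2. Leave clinical stopping decisions unchanged. Reword 10.2 so that worsening or intolerance stops study drug rather than study participation, and align it with 3.3, and with the dose adjustments in 2.2 and 4.2. Invite these participants to the scheduled week-6 assessments and record any new treatment.
3. Analyse the retrieved values in the randomised arm as a treatment-policy estimate. Report alongside it an on-drug analysis for MADRS as well as for cytokines, connectivity and cognition. In that analysis, set off-drug values to missing and, for MADRS, impute them from the interim scores.

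The cost is protocol wording and a few week-6 visits that are already scheduled and in the payment list (Section 3.2). The downside is that retrieved values may reflect stopped drug or new treatment and so dilute the treatment-policy difference (step 6). This is why both analyses are needed and should be labelled as answering different questions.
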